## 8.4 Procedure(s) to account for missing or spurious data

In the event of missing data, the study co-ordinator and chief investigator will contact the investigator collecting data. Missing data will be minimised by careful data management. Missing data will be described with reasons given where available; the number and percentage of individuals in the missing category will be presented. All data collected on data collection forms will be used, since only essential data items will be collected. No data will be considered spurious in the analysis since all data will be checked and cleaned before analysis.

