## **STUDY SUMMARY**

Full title		The impact of COVID-19 pandemic on the provision, practice and outcomes of vascular surgery			
Short title	COVER	COVER			
Aim	Assess the impact of COVII	Assess the impact of COVID-19 on vascular surgery			
Design	Multicentre Cohort Study	Multicentre Cohort Study			
Participants	•	All patients with a vascular pathology idenfied and treated during the COVID-19 pandemic			
Sample size	200 participants - ESTIMAT	200 participants - ESTIMATED			
Planned project period	24 months - ESTIMATED	24 months - ESTIMATED			
	Objectives	Outcome Measures			
Primary	Assess how the COVID-19 pandemic has changed the provision of vascular services in the UK	Collect data regarding the types of procedures performed in vascular units.			
Secondary	Assess how the COVID-19	Collect data regarding			

Key Words: Coronavirus, Cohort study, Outcomes, Vascular, Surgery

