## **Secondary Outcomes:**

To collect longitudinal data to identify condition-specific outcomes for these patients at 3, 6 months and 1 year.

- Example condition specific outcome measures to include:
- CLTI limb salvage, amputation free survival, all-cause mortality
- Carotid disease ipsilateral stroke rate, any stroke rate, all-cause mortality
- AAA aneurysm-related mortality, all-cause mortality
- AAS complication rate including ruptures, all-cause mortality.

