## 8.3 Statistical analysis plan

We will report absolute numbers of patients having each procedure during this observational study period. We will report proportion of patients dying or having amputation at 3, 6, and 12 months. No comparisons will be made.

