#### 12. ETHICAL AND REGULATORY CONSIDERATIONS

#### 12.1 Ethical approval and research governance

The study will be conducted in compliance with the principles of the ICH GCP guidelines and in accordance with all applicable regulatory guidance, including, but not limited to, the UK policy framework for health and social care research. Ethical approval for this study will be sought from the Research Ethics Committee combined with Health Research Authority (HRA) approval. No study activities will commence until favourable ethical opinion and HRA approval has been obtained. Progress reports and a final report at the conclusion of the trial will be submitted to the approving REC within the timelines defined by the

committee. Confirmation of capacity and capability will be obtained from the R&D department prior to commencement of the study at all participating sites.

Successful ethical approval for the UK was granted on the 2nd of April 2020 (Rec Reference: 20/NW/0196 Liverpool Central) for study Tiers 2 and 3. HRA approval was granted on the 3rd of April 2020. The approval mandates patient consent for tier 2 in order to capture procedural data and follow-up. Tier 3 was deemed not to require specific consent from the participant as often these are based on referred information and there is likely to be no direct patient contact.

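### The 3-, 6- and 12-month death-or-amputation figures are crude proportions with no stated denominator, so the 12-month figure is open to bias if follow-up is incomplete

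*Protocol*

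**What the plan says.** Section 8.3, which is itself headed as the statistical analysis plan, gives the outcome analysis in one sentence: "We will report proportion of patients dying or having amputation at 3, 6, and 12 months". It adds "No comparisons will be made". It states no denominator, confidence interval or method for patients whose status is unknown.

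Section 8.4 deals with missing data in three ways. For retrieval, "the study co-ordinator and chief investigator will contact the investigator collecting data". For description, "Missing data will be described with reasons given where available". For reporting, "the number and percentage of individuals in the missing category will be presented". These rules cover all variables, and none is specific to outcomes. The section also says that all collected data will be used.

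The Tier 3 secondary outcomes include "CLTI limb salvage, amputation free survival, all-cause mortality". Amputation-free survival is a time-to-event quantity.

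On timing, the Tier 2 outcomes in section 7 are listed for 3, 6 and 12 months, and Table 1 shows the same times. The closing paragraph of the Tier 2 outcomes, however, describes local collection at three and six months only. Section 7.4 ends the study 12 months after the last patient is included, so every patient has 12 months of potential follow-up.

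**The concern.** Death and amputation are permanent. A patient with an event by 3 months has a known 12-month result whatever happens to follow-up afterwards. A patient who is event-free at 3 months and then lost does not. A proportion at 12 months therefore needs a rule for the second patient, and the protocol gives none. Each of the two obvious rules can mislead:

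- Keeping such patients in the denominator treats them as event-free to 12 months.
- Dropping them, while keeping patients whose event came before any loss, removes event-free patients selectively.

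The distortion builds up with time, so the 3-, 6- and 12-month figures may not read as one course. Outcomes for patients presenting in the pandemic are part of the overall objective in section 3.1. With no comparisons planned, these descriptive figures are the outcome result.

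Gaps at 12 months are foreseeable from the document itself, because the Tier 2 text describes no local collection at that time.

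**Working it through.** There is no figure in the plan to reproduce. The Study Summary gives "200 participants - ESTIMATED", and section 8.1 says that no calculation was possible. The protocol states no event rate or loss rate, so every rate below is an assumption.

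**Inputs (assumed).** Event risks are 10% in months 0–3, 5% in months 3–6 and 6% in months 6–12. A share l of patients still event-free and in follow-up is lost for good in each interval, before status is recorded and independently of outcome.

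**True 12-month risk.** 1 − 0.90 × 0.95 × 0.94 = 1 − 0.8037 = 19.6%.

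**Worked case, l = 10%, per enrolled patient.**

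- Months 0–3: known 0.9000, events 0.0900, event-free 0.8100.
- Months 3–6: known 0.8100 × 0.90 = 0.7290, events 0.03645, event-free 0.69255.
- Months 6–12: known 0.69255 × 0.90 = 0.62330, events 0.03740, event-free 0.58590.
- Recorded events: 0.0900 + 0.03645 + 0.03740 = 0.1638.
- Known 12-month status: 0.1638 + 0.5859 = 0.7497, so 25.0% are unknown.

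**Estimates at 12 months.**

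- All enrolled as denominator: 0.1638 / 1 = 16.4%, or 17% too low in relative terms.
- Known status as denominator: 0.1638 / 0.7497 = 21.9%, or 11% too high.
- Life table: 1 − product of (1 − events / known in the interval) = 1 − 0.90 × 0.95 × 0.94 = 19.6%.
- Range with unknowns all event-free to all with an event: 16.4% to 16.4% + 25.0% = 41.4%.

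**Course over time in the same case.** The true risk is 10.0%, 14.5% and 19.6% at 3, 6 and 12 months. Known status gives 0.09/0.90 = 10.0%, then 0.12645/0.819 = 15.4%, then 21.9%. It starts correct and drifts upward. All enrolled gives 9.0%, 12.6% and 16.4%.

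**Other loss rates.**

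| Loss per interval | Unknown at 12 months | All enrolled | Known status | Life table |
|---|---|---|---|---|
| 5% | 13% | 18.0% | 20.7% | 19.6% |
| 10% | 25% | 16.4% | 21.9% | 19.6% |
| 15% | 36% | 14.9% | 23.2% | 19.6% |

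**Check with a different model.** With constant event and loss hazards, a true risk of 20% and a 20% chance of loss by 12 months (18% end unknown), the two proportions are 18.0% and 22.0%. The pattern does not depend on the interval set-up.

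**When the known-status proportion is right.** If 12-month status is missing independently of outcome, with earlier events as likely to be missing as event-free status, it is unbiased: 20.0% against a true 20%. If 20% are unknown and their risk is twice that of the known group, it is 0.20 / (0.8 + 0.2 × 2) = 16.7%. If their risk is half, it is 0.20 / (0.8 + 0.2 × 0.5) = 22.2%.

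**Sampling error for scale.** With 200 patients and a risk of 20%, the 95% half-width is 1.96 × √(0.2 × 0.8 / 200) = 5.5 points.

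**The case against.** A reader might infer that section 8.4 counts patients of unknown status as event-free, and hence that the 12-month figures are certain to be biased. The text does not support this. Section 8.4 is a general reporting rule, and showing the missing as their own category is not the same as calling them event-free. The denominator is unstated, not wrongly fixed. Section 8.4 also provides for site queries and reasons for missingness, which may keep gaps small.

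A reader might also infer that Tier 3 loss will be related to outcome, because section 12.1 says "often these are based on referred information and there is likely to be no direct patient contact". That sentence explains why consent is not needed and says nothing about completeness of follow-up. Nowhere does the protocol say that discharged or palliated patients are harder to trace.

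Other points on that side also carry weight:

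- Section 7.4 rules out planned administrative censoring before 12 months.
- Outcomes are collected locally and hospital records are a source, so an early gap may be filled later. The upward bias needs permanent loss.
- At 13% unknown the errors are under two points either way, well inside the sampling half-width.
- The 3-, 6- and 12-month outcomes are secondary within Tiers 2 and 3.
- A life table does not cure loss that is related to outcome.
- A fuller analysis plan may exist and could state the denominator.

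The last point does not dispose of the matter. Section 8.3 names an estimator, and a later plan would have to replace it, not merely add detail.

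**Conclusion.** The point holds in conditional form, as an inexpensive improvement. The stated estimator is a crude proportion of permanent events with no denominator, and nothing in 8.4 settles how unknown status is treated. If patients are permanently lost, an all-enrolled denominator understates the 12-month risk and a known-status denominator overstates it, even when loss is random.

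Under the assumed 19.6% risk and 25% unknown, the errors are about 3 points down or 2 points up. They shrink toward zero as follow-up approaches completeness. The direction and size in this study cannot be known from the protocol, and no certain bias is claimed. The firmest evidence in the document that 12-month gaps may arise is the mismatch in the Tier 2 text on collection times.

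**What to change.** **Section 8.3.** Report life-table estimates (Kaplan-Meier where event dates exist) of death and of death-or-amputation at 3, 6 and 12 months, with 95% confidence intervals, censoring each patient at the last known status. From status at each time point alone, risk = 1 − product of (1 − events / patients with known status in the interval). For amputation alone, use the cumulative incidence with death as a competing event. Show the raw counts alongside.

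**Section 8.4.** State that patients of unknown status are not counted as event-free. Add a best/worst-case range (all unknowns event-free to all with an event), because the life table assumes that loss is unrelated to outcome.

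**Section 7, Tier 2 outcomes.** Reconcile the list of outcomes at 3, 6 and 12 months with the description of local collection at three and six months.

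**Cost.** Wording and a little more analysis, with no extra patients or data items. Intervals are slightly wider. In the worked case with 200 patients, the numbers with known status in the three intervals are 180, 145.8 and 124.7, with 18, 7.29 and 7.48 events. Greenwood's sum of events / (known × event-free) is 0.000617 + 0.000361 + 0.000512 = 0.00149, so the half-width is 1.96 × 0.8037 × √0.00149 = 6.1 points. With complete follow-up it would be 1.96 × √(0.1963 × 0.8037 / 200) = 5.5 points.

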## 9. DATA MANAGEMENT

## 9.1 Data collection tools and source document identification

All data will be collected prospectively using a purpose built electronic database, using the REDCap platform, which is overseen by the University of Birmingham (main contact: [name]). Data will be collected and uploaded by senior surgical trainees with appropriate research and REDCap training, from the VERN collaborative, for both Tiers 2 and 3.

## 9.2 Data handling and record keeping

A specific study number will be assigned to each patient to allow anonymised data to be collected using a purpose built REDCap platform that will be accessible at each centre.

The CRFs will be completed by the investigators at each site, aiming to complete data collection within one day after the patient has been discharged home. Data will be entered onto the REDCap web platform, which will be purpose built for

this study using secure NHS servers and procedures which have been tested, validated and are widely used for NHS research of this nature. Investigators will receive relevant training at the site initiation visits. The participants will be identified by a study specific participant's number and/or code in any database. The name and any other identifying detail will not be included in any study data electronic file. The patient's name will be visible on their consent form which will be stored in an NHS institution at each study site as per NHS and GCP guidance. Each patient will be assigned their unique identifying number once recruited and if applicable, this will be linked to their consent form at the originating site. No further patient details will be shared on REDCap or between centres. Patients' names, date of birth, address or any other identifier (including contact details) will not be shared on REDCap.

## 9.3 Source data and access to data

Source documents are original documents, data, and records from which participants' CRF data are obtained. These include, but are not limited to, hospital records (from which medical history and previous and concurrent medication may be summarised into the CRF), clinical and office charts, laboratory and pharmacy records, diaries, microfiches, radiographs, and correspondence. CRF entries will be considered source data if the CRF is the site of the original recording (e.g. there is no other written or electronic record of data). All documents will be stored safely in confidential conditions. On all study-specific documents, other than the signed consent, the participant will be referred to by the study participant number, not by name. The persons designated to collect data for this study may collect data using a printed CRF anonymously (using only the study identification number and no other patient identifiable data) but are required to input the data on the electronic data collection software (REDCap) within the space of 24 hours (1 calendar day).

Direct access will be granted to authorised representatives from the Sponsor, host institution and the regulatory authorities to permit monitoring, audits and inspections.

The study staff will ensure that the participants' anonymity is maintained. The participants will be identified only by initials and a participants ID number on the CRF and any electronic database. All documents will be stored securely and only accessible by study staff and authorised personnel. The study will comply with the Data Protection Act which requires data to be anonymised as soon as it is practical to do so.

#### 9.4 Archiving

Following the resolution of queries and confirmation of study close-out by the Chief Investigator, all essential documentation will transferred to a third party archiving service, which provides suitable fire and water-resistant facilities. Study files will be archived for a period of 25 years. Access to the study

documentation will be restricted to named individuals within the study team with express permission from the Chief Investigator.

#### 10. TRIAL OVERSIGHT

## 10.1 Role and responsibilities of the Sponsor

UHCW has agreed to act as sponsor for this trial and will undertake the responsibilities of sponsor as defined by the UK Policy Framework for Health and Social Care Research and ICH Good Clinical Practice. An authorised representative of the Sponsor has approved the final version of this protocol with respect to the trial design, conduct, data analysis and interpretation and plans for publication and dissemination of results. As sponsor, UHCW provides indemnity for this study and, as such, will be responsible for claims for any negligent harm suffered by anyone as a result of participating in this study. The indemnity is renewed on an annual basis and will continue for the duration of this study.

## 10.2 Role and responsibilities of the Funder

Funding for this study is provided by Vascular Society of Great Britain and Ireland. The NIHR funds the salary of [name] – co-CI.

## 10.3 Trial Management Arrangements

This study will be managed by the Vascular and Endovascular Research Network (VERN) with monthly remote teleconferencing calls with the CI and research team i.e. [name], [name], and [name].

## Study Co-ordinator / Manager:

[name] i.e. The Study Co-ordinator / Manager will have responsibility for overseeing day to day coordination of the study. The relevant responsibilities include but are not limited to:

- Coordinating protocol development, patient and management documents
- Correspondence with study funders
- Setting up and maintaining the Master File
- Ensuring necessary approvals are in place before the start of the trial at each site
- Providing training to personnel
- Providing data management support; including data input, maintenance of the trial database and raising of queries
- Producing progress reports and coordinating TSC meetings and minutes
- Ensuring data security and quality and ensuring data protection laws are adhered to
- Ensuring complete records are in place for audit and monitoring purposes

- Ensuring the study is conducted in accordance with the ICH GCP
- Archiving all original documents including the data forms in line with UHCW NHS Trust policy.

## 10.3.1 Principal Investigators

"Site Principal Investigator responsibilities include, but are not limited to:

- Ensuring that the study is conducted as set out in the protocol and supporting documents
- Delegating study related responsibilities only to suitably trained and qualified personnel and ensuring that those with delegated responsibilities fully understand and agree to the duties being delegated to them
- Ensuring that CVs and evidence of appropriate training for all Site staff are available in the Site File
- Ensuring that all delegated duties are captured in the Delegation Log
- Ensuring all Adverse Events are documented and reported promptly to the Manager
- Ensuring the study is conducted in accordance with ICH GCP principles
- Allowing access to source data for monitoring, audit and inspection
- Ensuring that all source data is complete and provided to the Manager at regular intervals.

## 11. MONITORING, AUDIT & INSPECTION

The study may be monitored by the Research & Development Department at UHCW as representatives of the Sponsor, to ensure that the study is being conducted as per protocol, adhering to Research Governance and GCP. The approach to, and extent of, monitoring may be specified in a monitoring plan determined by the risk assessment undertaken prior to the start of the study.

#### 12. ETHICAL AND REGULATORY CONSIDERATIONS

#### 12.1 Ethical approval and research governance

The study will be conducted in compliance with the principles of the ICH GCP guidelines and in accordance with all applicable regulatory guidance, including, but not limited to, the UK policy framework for health and social care research. Ethical approval for this study will be sought from the Research Ethics Committee combined with Health Research Authority (HRA) approval. No study activities will commence until favourable ethical opinion and HRA approval has been obtained. Progress reports and a final report at the conclusion of the trial will be submitted to the approving REC within the timelines defined by the

committee. Confirmation of capacity and capability will be obtained from the R&D department prior to commencement of the study at all participating sites.

Successful ethical approval for the UK was granted on the 2nd of April 2020 (Rec Reference: 20/NW/0196 Liverpool Central) for study Tiers 2 and 3. HRA approval was granted on the 3rd of April 2020. The approval mandates patient consent for tier 2 in order to capture procedural data and follow-up. Tier 3 was deemed not to require specific consent from the participant as often these are based on referred information and there is likely to be no direct patient contact.

#### 12.2 Peer review

The study has been reviewed by all VERN members (12 executive committee members), including nurses and doctors.

#### 12.3 Public and Patient Involvement

The study has been discussed with a patient via the VERN executive committee, who has approved the design and conduct.

#### 12.4 Data protection and patient confidentiality

The study will comply with the current Data Protection regulations and regular checks and monitoring will be undertaken by the Trial Manger to ensure compliance. Participants will be assigned a unique identifier upon enrolment in to the study to allow pseudonymisation of patient-identifiable data. Access to patient identifiable data will be restricted to members of the study co-ordination team who require it for the performance of their role. Electronic data will be stored on password protected encrypted drives and hard copies of study documents will be stored in locked filing cabinets in secure entry-card protected sites.

#### 13. DISSEMINATION POLICY

Findings will be emailed to the Vascular Society of Great Britain and Ireland and the National Vascular Registry will be informed. Finally, an abstract will be submitted for presentation at the annual VSGBI Conference.

Collaborators from each site who contribute patients will be recognised on any resulting publications as PubMed-citable co-authors. The VERN model for collaborative authorship that will be used for any outputs arising from this project can be found here: https://vascular-research.net/authorship-policy/.

An example of this can be found here: https://pubmed.ncbi.nlm.nih.gov/29452941.
